#### **Trademark Information**

Trademarks of the GlaxoSmithKline group of companies

NUCALA

Trademarks not owned by the GlaxoSmithKline group of companies

SAS

Xolair (omalizumab)

Ypsomed AG

## 12.2. Appendix 2: Anaphylaxis Criteria

Joint NIAID/FAAN Second Symposium on Anaphylaxis [Sampson, 2006]. The criteria do not make a distinction based on underlying mechanism. These criteria are summarized as follows:

- 1) Acute onset of an illness (minutes to several hours) with involvement of the skin, mucosal tissue, or both (e.g., generalized hives, pruritus or flushing, swollen lipstongue-uvula), and at least one of the following:
  - a) Respiratory compromise (e.g., dyspnea, wheeze-bronchospasm, stridor, reduced peak expiratory flow [PEF], hypoxemia)
  - b) Reduced blood pressure (BP) or associated symptoms of end-organ dysfunction (e.g., hypotonia [collapse], syncope, incontinence)
- 2) Two or more of the following that occur rapidly after exposure to a likely allergen for that patient (minutes to several hours):
  - a) Involvement of the skin-mucosal tissue (e.g., generalized hives, itch-flush, swollen lips-tongue-uvula)
  - b) Respiratory compromise (e.g., dyspnea, wheeze-bronchospasm, stridor, reduced PEF, hypoxemia)
  - c) Reduced BP or associated symptoms (e.g., hypotonia [collapse], syncope, incontinence)
  - d) Persistent gastrointestinal symptoms (e.g., crampy abdominal pain, vomiting)
- 3) Reduced BP after exposure to known allergen for that patient (minutes to several hours):
  - a) Infants and children: low systolic BP (age specific) or greater than 30% decrease in systolic BP
  - b) Adults: systolic BP of less than 90 mm Hg or greater than 30% decrease from that person's baseline

#### 12.3. Appendix 3: Modified List of Highly Effective Methods for Avoiding Pregnancy in FRP and Collection of Pregnancy Information

#### 12.3.1. Definition of post menopausal female

Post menopausal female is defined as:

- Females 60 years of age or older
- Menopause is the phase associated with complete cessation of menstrual cycles and implies the loss of reproductive potential by ovarian failure. This typically occurs around 50 years of age, although it may occur earlier or later. A practical definition accepts menopause after 1 year without menses with an appropriate clinical profile, e.g., age appropriate, >45 years, in the absence of hormone replacement therapy (HRT) or medical suppression of the menstrual cycle (e.g., leuprolide treatment).
- In questionable cases for women < 60 years of age, a blood sample with simultaneous follicle stimulating hormone and estradiol falling into the central laboratory's postmenopausal reference range is confirmatory (these levels need to be adjusted for specific laboratories/assays) [Kronenberg, 2008; Strauss, 2004].
- Females under 60 years of age, who are on HRT and wish to continue, and whose menopausal status is in doubt, are required to use a highly effective method to avoid pregnancy, as outlined in the protocol. Otherwise, they must discontinue HRT to allow confirmation of post-menopausal status prior to study enrolment. For most forms of HRT, at least 2 to 4 weeks will elapse between the cessation of therapy and the blood draw; this interval depends on the type and dosage of HRT. Following confirmation of their post-menopausal status, they can resume use of HRT during the study without use of a highly effective method to avoid pregnancy. If laboratory values for FSH and estradiol are drawn and the results do not confirm menopausal defined above without question, the subject may still enrol in the study as a FNRP if approved by the GSK Medical Monitor and the safety physician.

# 12.3.2. Modified List of Highly Effective Methods for Avoiding Pregnancy in Females of Reproductive Potential (FRP)

The list does not apply to FRP with same sex partners or for subjects who are and will continue to be abstinent from penile-vaginal intercourse on a long term and persistent basis, when this is their preferred and usual lifestyle. Periodic abstinence (e.g. calendar, ovulation, symptothermal, post-ovulation methods) and withdrawal are not acceptable methods of contraception.

- 1. Contraceptive subdermal implant
- 2. Intrauterine device or intrauterine system
- 3. Combined estrogen and progestogen oral contraceptive [Hatcher, 2011])
- 4. Injectable progestogen [Hatcher, 2011]

- 5. Contraceptive vaginal ring [Hatcher, 2011]
- 6. Percutaneous contraceptive patches [Hatcher, 2011]
- 7. Male partner sterilization with documentation of azoospermia prior to the female subject's entry into the study, and this male is the sole partner for that subject [Hatcher, 2011]. The documentation on male sterility can come from the site personnel's: review of subject's medical records, medical examination and/or semen analysis, or medical history interview provided by her or her partner.

These allowed methods of contraception are only effective when used consistently, correctly and in accordance with the product label. The investigator is responsible for ensuring that subjects understand how to properly use these methods of contraception.

#### 12.3.3. Collection of Pregnancy Information

- Investigator will collect pregnancy information on any female subject, who becomes pregnant while participating in this study
- Information will be recorded on the appropriate form and submitted to GSK within 2 weeks of learning of a subject's pregnancy.
- Subject will be followed to determine the outcome of the pregnancy. The investigator will collect follow up information on mother and infant, which will be forwarded to GSK. Generally, follow-up will not be required for longer than 6 to 8 weeks beyond the estimated delivery date.
- Any termination of pregnancy will be reported, regardless of fetal status (presence or absence of anomalies) or indication for procedure.
- While pregnancy itself is not considered to be an AE or SAE, any pregnancy complication or elective termination of a pregnancy will be reported as an AE or SAE.
- A spontaneous abortion is always considered to be an SAE and will be reported as such.
- Any SAE occurring as a result of a post-study pregnancy which is considered reasonably related to the study treatment by the investigator, will be reported to GSK as described in Appendix 6. While the investigator is not obligated to actively seek this information in former study participants, he or she may learn of an SAE through spontaneous reporting.

# 12.4. Appendix 4: Liver Safety Required Actions and Follow up Assessments

# 12.4.1. Liver chemistry stopping criteria and required follow up assessments

	Liver Chemistry Stopping Criteria - Liver Stopping Event				
ALT-absolute	$ALT \ge 8xULN$				
ALT Increase	ALT $\ge$ 5xULN but <8xULN persists for $\ge$ 2 weeks ALT $\ge$ 3xULN but <5xULN persists for $\ge$ 4 weeks				
Bilirubin 	ALT $\ge$ 3xULN and bilirubin $\ge$ 2xULN (>35% direct bilirubin)				
INR 	ALT $\geq$ 3xULN and INR>1.5, if INR measured				
Cannot Monitor	ALT $\ge$ 5xULN but <8xULN and cannot be monitored weekly for $\ge$ 2 weeks ALT $\ge$ 3xULN but <5xULN and cannot be monitored weekly for $\ge$ 4 weeks				
Symptomatic 	ALT $\geq$ 3xULN associated with symptoms (new or worsening) believed to be related to liver injury or hypersensitivity				
Required Actions and Follow up Assessments following ANY Liver Stopping Event					

	Actions		Follow Up Assessments
•	Immediately discontinue study treatment	•	Viral hepatitis serology 
•	Report the event to GSK within 24 hours	•	Only in those with underlying chronic
•	Complete the liver event CRF and complete an SAE data collection tool if the event also meets the criteria for an SAE 		hepatitis B at study entry (identified by positive hepatitis B surface antigen) quantitative hepatitis B DNA and hepatitis delta antibody  .
•	Perform liver event follow up assessments	•	Blood sample for pharmacokinetic (PK)
•	Monitor the subject until liver chemistries resolve , stabilize, or return to within baseline		analysis, obtained within 4 weeks after last dose 
•	(see MONITORING below) Do not restart/rechallenge subject with	•	Serum creatine phosphokinase (CPK) and lactate dehydrogenase (LDH).
	study treatment. Permanently discontinue study treatment and may continue subject in the study for any protocol specified follow up	•	Fractionate bilirubin, if total bilirubin≥2xULN
	assessments	•	Obtain complete blood count with differential to assess eosinophilia. Note: the mechanism of action of mepolizumab leads to lowering of eosinophils.

MO For	NITORING: bilirubin or INR criteria: Repeat liver chemistries (include ALT, AST, alkaline phosphatase, bilirubin) and perform liver event follow up assessments within 24 hrs	•	Record the appearance or worsening of clinical symptoms of liver injury, or hypersensitivity, on the AE report form Record use of concomitant medications on the concomitant medications report form including acetaminophen, herbal remedies, other over the counter medications.
•	Monitor subjects twice weekly until liver chemistries resolve, stabilize or return to within baseline	•	Record alcohol use on the liver event alcohol intake case report form
•	A specialist or hepatology consultation is recommended	Foi	r bilirubin or INR criteria:
•	All other criteria: Repeat liver chemistries (include ALT, AST, alkaline phosphatase, bilirubin) and perform liver event follow up assessments within 24- 72 hrs Monitor subjects weekly until liver chemistries resolve, stabilize or return to within baseline	•	Anti-nuclear antibody, anti-smooth muscle antibody, Type 1 anti-liver kidney microsomal antibodies, and quantitative total immunoglobulin G (IgG or gamma globulins). Serum acetaminophen adduct HPLC assay (quantifies potential acetaminophen contribution to liver injury in subjects with definite or likely acetaminophen use in the preceding week [James, 2009]). NOTE: not required in China
		•	Liver imaging (ultrasound, magnetic resonance, or computerised tomography) and /or liver biopsy to evaluate liver disease  complete Liver Imaging and/or Liver Biopsy CRF forms.

- Serum bilirubin fractionation should be performed if testing is available. If serum bilirubin fractionation is not immediately available, discontinue study treatment for that subject if ALT ≥ 3xULN and bilirubin ≥ 2xULN. Additionally, if serum bilirubin fractionation testing is unavailable, record presence of detectable urinary bilirubin on dipstick, indicating direct bilirubin elevations and suggesting liver injury.
- All events of ALT ≥ 3xULN and bilirubin ≥ 2xULN (>35% direct bilirubin) or ALT ≥ 3xULN and INR>1.5, if INR
  measured which may indicate severe liver injury (possible 'Hy's Law'), must be reported as an SAE (excluding
  studies of hepatic impairment or cirrhosis); INR measurement is not required and the threshold value stated
  will not apply to subjects receiving anticoagulants
- New or worsening symptoms believed to be related to liver injury (such as fatigue, nausea, vomiting, right upper quadrant pain or tenderness, or jaundice) or believed to be related to hypersensitivity (such as fever, rash or eosinophilia)
- Includes: Hepatitis A IgM antibody; Hepatitis B surface antigen and Hepatitis B Core Antibody (IgM); Hepatitis C RNA; Cytomegalovirus IgM antibody; Epstein-Barr viral capsid antigen IgM antibody (or if unavailable, obtain heterophile antibody or monospot testing); Hepatitis E IgM antibody
- 5. If hepatitis delta antibody assay cannot be performed,, it can be replaced with a PCR of hepatitis D RNA virus (where needed) [Le Gal, 2005].
- 6. PK sample may not be required for subjects known to be receiving placebo or non-GSK comparator treatments. Record the date/time of the PK blood sample draw and the date/time of the last dose of study treatment prior to blood sample draw on the CRF. If the date or time of the last dose is unclear, provide the subject's best

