## 5.5.1. Withdrawal from the Study

Subjects who have withdrawn from the study should complete assessments for the Early Withdrawal Visit, 4 weeks after the last dose of mepolizumab (see Time and Events Table, Section 7.1).

A reason for the withdrawal from the study must be captured in the eCRF.

A subject must be discontinued if any of the following criteria are met:

- Withdrawal of consent
- Lost to follow-up

A subject will also be withdrawn from the study, in consultation with the medical monitor and principal investigator, if any of the following stopping criteria are met:

- Laboratory parameters: Clinically important changes in laboratory parameters identified
- ECG: Clinically significant abnormality identified during the study that meet the QTc stopping criteria described in Section 5.5.3
- Liver Chemistry: Meets any of the Liver chemistry stopping criteria (see Section 5.5.2 and Appendix 4
- Pregnancy: Positive pregnancy test (see Appendix 3). Pregnancy and pregnancy outcomes of subjects exposed to mepolizumab will be followed

The following actions must be taken in relation to a subject who fails to attend the clinic for a required study visit:

- The site must attempt to contact the subject and re-schedule the missed visit as soon as possible.
- The site must counsel the subject on the importance of maintaining the assigned visit schedule and ascertain whether or not the subject wishes to and/or should continue in the study.

- In cases where the subject is deemed 'lost to follow up', the investigator or designee must make every effort to regain contact with the subject (where possible, 3 telephone calls and if necessary a certified letter to the subject's last known mailing address or local equivalent methods). These contact attempts should be documented in the subject's medical record.
- Should the subject continue to be unreachable, only then will he/she be considered to have withdrawn from the study with a primary reason of "Lost to Follow-up".

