## Liver Chemistry Increased Monitoring Algorithm with Continued Therapy for ALT ≥3xULN but <8xULN

\*INR value not applicable to subjects on anticoagulants

Required actions and follow-up assessment for all subjects who meet liver chemistry stopping or monitoring criteria are defined in Appendix 4.

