# 12.4.2. Liver chemistry increased monitoring criteria with continued therapy

Liver Chemistry Increased Monitoring Criteria – Liver Monitoring Event				
Criteria	Actions			
ALT ≥5xULN and <8xULN and bilirubin <2xULN without symptoms believed to be related to liver injury or hypersensitivity, and who can be monitored weekly for 2 weeks. OR ALT ≥3xULN and <5xULN and bilirubin <2xULN without symptoms believed to be related to liver injury or hypersensitivity, and who can be monitored weekly for 4 weeks.	
 
Notify the GSK medical monitor within 24 hours of learning of the abnormality to discuss subject safety.
 
			
	
 
Subject can continue study treatment
 
Subject must return weakly for ropeat liver
 
			
	
 
Subject must return weekly for repeat iver chemistries (ALT, AST, alkaline phosphatase, bilirubin) until they resolve, stabilise or return to within baseline
 
			
	
 
If at any time subject meets the liver chemistry stopping criteria, proceed as described above
 
			
	
 
If ALT decreases from ALT ≥5xULN and <8xULN to ≥3xULN but <5xULN, continue to monitor liver chemistries weekly.
 
			
	
 
If, after 4 weeks of monitoring, ALT <3xULN and bilirubin <2xULN, monitor subjects twice monthly until liver chemistries normalize or return to within baseline.
 
			

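### As worded in Appendix 4, the 4-week ALT stop ends at 5xULN and carries no time across it, so weekly 4, 4, 6, 4, 4xULN meets neither persistence stop at week 4 while a steady 4xULN must stop

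*Protocol*

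**What the plan says.** Protocol 12.4.1 (Appendix 4) defines the stopping events. Two of them depend on duration:

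- ALT at or above "5xULN but <8xULN persists for" 2 weeks or more.
- ALT at or above "3xULN but <5xULN persists for" 4 weeks or more.

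Each band has an upper limit. Other stops act without a duration condition: ALT ≥8xULN, and ALT ≥3xULN with raised bilirubin, with INR above 1.5 (if measured), or with symptoms. A subject whose ALT lies in one of the two bands and who cannot be monitored weekly must also stop. Any stopping event requires immediate and permanent discontinuation, a report within 24 hours, a liver event CRF, and the instruction to "Perform liver event follow up assessments", which include viral serology, CPK, LDH and a PK sample. Section 5.5.2.1 rules out any restart.

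Section 12.4.2 covers the same two bands when bilirubin is below 2xULN, there are no symptoms and weekly monitoring is possible. The medical monitor is notified within 24 hours, chemistry is repeated weekly, and "Subject can continue study treatment". For a fall from the upper to the lower band, the only instruction is to "continue to monitor liver chemistries weekly". A later bullet, beginning "If, after 4 weeks of monitoring, ALT", relaxes monitoring only if ALT is below 3xULN and bilirubin below 2xULN.

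Section 5.5.2 contains flowcharts that are not visible in the text available for review. It then says: "Required actions and follow-up assessment for all subjects who meet liver chemistry stopping or monitoring criteria are defined in Appendix 4".

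**The concern.** A stopping rule should not treat a worse course more leniently than a milder one. Because the 4-week band ends at 5xULN, a value of 6xULN lies outside it and interrupts the run. Nothing in 12.4.1 or 12.4.2 says that time at ≥5xULN counts towards the 4 weeks, or that the 4 weeks run from the first ALT ≥3xULN. Two subjects can therefore have ALT ≥3xULN for the same time, and the one whose values are never lower and once higher escapes the mandatory stop.

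Two things are at stake. One is the discontinuation itself. The other is the liver work-up in 12.4.1, which is tied to a stopping event and is not among the actions listed for a monitoring event in 12.4.2. The classification also reaches the report, because SAP 11.2 summarises liver stopping and monitoring events if any occur.

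**Working it through.** **Inputs.** The two bands and durations are those in 12.4.1. Weekly testing comes from 12.4.2. The visit windows (Visit 3 at Week 4 ±7 days, Visit 4 at Week 8 ±7 days) come from Section 7.1. The documents give no rate for such courses and no worked example, so there is no figure of the plan's own to reproduce.

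**Assumptions.** Week 0 is the first ALT ≥3xULN. There are no symptoms, bilirubin is <2xULN, INR is not raised, and weekly tests are done. The protocol does not define how persistence is measured, so two conventions are used:

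- *Elapsed time:* first to last value of an unbroken in-band run. 2 weeks needs 3 weekly values; 4 weeks needs 5.
- *Count:* k weekly values count as k weeks. 2 weeks needs 2 values; 4 weeks needs 4.

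The stop week is the first week that completes a qualifying run. With s the first week of the run and w the required weeks, it is s + w by elapsed time and s + w − 1 by count.

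**The example, 4, 4, 6, 4, 4xULN.** The lower band holds two runs (weeks 0–1 and 3–4), each spanning 1 week with 2 values. The upper band holds one value (week 2). Neither criterion is met at week 4 under either convention. If ALT then stays at 4xULN, the qualifying lower-band run starts at week 3. It completes at 3 + 4 = week 7 by elapsed time, or 3 + 4 − 1 = week 6 by count.

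| Weekly ALT (xULN) | Now: elapsed | Now: count | Fixed: elapsed | Fixed: count |
|---|---|---|---|---|
| Steady 4 | week 4 | week 3 | week 4 | week 3 |
| Steady 6 | week 2 | week 1 | week 2 | week 1 |
| 4, 4, 6, then 4s | week 7 | week 6 | week 4 | week 3 |
| Alternating 4, 6 | never | never | week 4 | week 3 |
| 5.5, 5.5, then 4.5s | week 6 | week 1 | week 4 | week 1 |
| 7, 5.5, 4, 3.5, 3.1, then <3 | never | week 1 | week 4 | week 1 |

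The example is delayed by 7 − 4 = 3 weeks by elapsed time and 6 − 3 = 3 weeks by count. A course that crosses 5xULN only once is delayed, relative to a steady 4xULN, by at most 2 weeks by elapsed time (6 − 4, as in the fifth row) and at most 1 week by count.

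**Dosing, for a rise first seen at Visit 3.** The relevant dose is dose 3 at Visit 4. I assume that a sample drawn at Visit 4 is not acted on before that day's dose.

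- *Elapsed time:* a steady 4xULN stops at Week 4 + 4 = Week 8, nominally the day of dose 3. Dose 3 can differ only if Visit 4 falls after that value. The largest gap is the latest Visit 4 (Week 9) minus the earliest Visit 3 plus 4 weeks (Week 3 + 4 = Week 7), which is 14 days.
- *Count:* a steady 4xULN stops at Week 4 + 3 = Week 7, before dose 3 at Week 8. The example stops at Week 4 + 6 = Week 10, after it. Dose 3 can therefore differ on the nominal schedule.

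**The case against.** The strongest objection is that part of the operative text cannot be seen. The 5.5.2 flowcharts are missing from the review copy, and the heading of the second one treats 3 to <8xULN as a single monitoring range. A reader might infer from Appendix 4 that the protocol nowhere combines the bands. The documents do not support that: the flowcharts may do so. What remains is that 5.5.2 sends the reader to Appendix 4 for the required actions, and the Appendix 4 wording does not combine them. If the flowcharts do, the two places disagree and Appendix 4 still needs the edit.

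Second, no sentence says that one value ≥5xULN restarts the 4-week clock, and the monitoring language in 12.4.2 suggests a single episode. A subject still at 4xULN after 4 weeks does not qualify for relaxed monitoring. That is fair as a guide to intent. It does not create a stop, because 12.4.2 refers back to the stopping criteria and the relevant one remains bounded at <5xULN.

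Third, other safeguards apply. A reader might infer that such a subject is dosed without oversight. That is not so. The medical monitor is notified within 24 hours, chemistry is weekly, and the remaining liver stops stay in force. Section 5.5.1 also provides for withdrawal, in consultation with the medical monitor and principal investigator, for "Clinically important changes in laboratory parameters identified". Section 7.7.7 asks for the cause of persistent clinically significant abnormalities to be identified, so a work-up may happen without a stopping event. These points stand and limit the importance. They rest on judgement, whereas the persistence stops are meant to be mandatory.

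Fourth, the fix has a price. The course 7, 5.5, 4, 3.5, 3.1, then <3xULN never stops now by elapsed time, but would be permanently stopped at week 4. This stands, and a reader should not infer that the fix merely brings stops forward. The current rule, however, already stops a course falling from 4.9 to 3.1xULN over the same 4 weeks, so it does not otherwise spare resolving courses.

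**Conclusion.** The point holds for the wording of Appendix 4. The two persistence criteria rank some courses the wrong way: the example stops 3 weeks later than a steady 4xULN under either convention, and a course alternating between 4 and 6xULN meets neither criterion at any time.

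The importance is minor. The course is constructed, the documents give no frequency, and such courses should be very rare. Entry requires ALT ≤2xULN at Visit 1 (Section 5.3), and treatment is three doses 4 weeks apart, so dosing would seldom change. It would be wrong, though, to say that dose 3 can differ only through the visit windows: that is true by elapsed time but not by count. The primary endpoint result is unaffected.

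The conclusion assumes weekly values, an unbroken run as the meaning of persistence, and that no other stop is triggered. Confidence is medium, because the 5.5.2 flowcharts could not be read.

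**What to change.** - In 12.4.1, reword the 4-week criterion to: *ALT ≥3xULN persists for ≥4 weeks (time at ≥5xULN counts)*. Keep the 2-week rule for ≥5xULN and the ≥8xULN stop.
- In 12.4.2, add to the band-change bullet that the 4 weeks run from the first ALT ≥3xULN.
- Check the 5.5.2 algorithms and align them if they differ.

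With this wording the example stops when a steady 4xULN does: week 4 by elapsed time, week 3 by count.

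The cost is one reworded line, one added line and one check. No extra tests are needed, because weekly chemistry is already required. The clinical downside is that a rare subject whose ALT is falling from the upper band stops 1 to 2 weeks earlier, or is permanently stopped when the current wording would not have stopped them. The sponsor should accept that explicitly when making the change.
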